### 2.2 Secondary Objectives include the following:

- 2.2.1 To determine if reduction in TMPRSS2 activity via direct inhibition with Camostat mesilate combined with SOC treatment will increase the proportion of patients alive and free of ventilator use or ECMO at Day 28 as compared to SOC treatment combined with placebo.
- 2.2.2 To determine if the combination of Camostat mesilate combined with SOC treatment will result in a decreased mortality rate at 28 and 56 days as compared to SOC treatment combined with placebo.
- 2.2.3 To determine if time to clinical improvement is reduced in patients receiving SOC treatment combined with Camostat mesilate as compared to SOC treatment combined with placebo.
- 2.2.4 To determine if Camostat mesilate combined with SOC treatment is associated with overall improved clinical status at Days 14 and 28 as compared to SOC treatment combined with placebo.
- 2.2.5 To determine if Camostat mesilate combined with SOC treatment is associated with a reduced length of stay in the hospital as compared to SOC treatment combined with placebo.
- 2.2.6 To determine if Camostat mesilate combined with SOC treatment is associated with reduced duration of:
  - a) mechanical ventilation or ECMO use,
  - b) non-invasive ventilation or high-flow oxygen use, and

- c) supplemental oxygen use as compared to SOC treatment combined with placebo.
- 2.2.7 To compare the safety and toxicity profile of Camostat mesilate combined with SOC treatment as compared to SOC treatment combined with placebo.
- 2.2.8 To determine if treatment with Camostat mesilate combined with SOC treatment is associated with decreased incidence of thrombotic events and bleeding complications as compared to SOC treatment combined with placebo.

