**5. Length of Stay:** Length of stay will be defined as the time from study entry until the time of hospital discharge and the number of days hospitalized will be compared between groups by use of non-parametric Wilcoxon rank-sum test. The proportions of patients who require an ICU admission will be compared between randomized groups by the use of independent samples Z-test for proportions and a 95% confidence interval will be constructed for the difference between groups. In addition, time in the ICU will be described in number of days spent receiving ICU care, if applicable.

**6. Duration of Mechanical ventilation / ECMO:** Duration of ventilator / ECMO use will be summarized by medians or quartiles by arm for those subjects who have a baseline score of 6-7 at study entry.

**7. Duration of non-invasive ventilation / high-flow oxygen:** Duration of non-invasive ventilation / high-flow oxygen will be summarized by medians and quartiles by arm for those patients who have a clinical status score of 5 at study entry.

**8. Duration of supplemental oxygen use:** Duration of supplemental oxygenation use will be summarized by medians and quartiles by arm for those patients who have a clinical status score greater than or equal to 4 at study entry.

**9. Occurrence of adverse events related to treatment:** Analyses for safety will include all participants who are randomized and received at least 1 dose of study treatment.

Participants will be grouped according to the treatment to which they were randomized. Events will be summarized on the basis of the date of onset for the event. The maximum grade for each type of adverse event will be recorded for each patient. Frequency tables of adverse events will be constructed based on maximum grade for each treatment arm. Overall adverse event rates, rates of grade 3 or higher events and serious adverse events will be compared between treatment groups using Chi-square or Fisher's exact test.

**10. Development of thrombosis / bleeding complications:** Incidence of arterial and venous thrombosis or bleeding complications will be described and compared by treatment arms by use of chi-square or Fisher's exact test.

Subgroup analyses for the primary and secondary analyses will examine the treatment effect across the following subgroups of interest. Forest plots with odds ratio and 95% confidence intervals will be presented along with interaction tests.

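### Objective 2.2.6 asks for a comparison with placebo on three durations of respiratory support, but 13.5 items 6–8 plan only medians and quartiles by arm, with no effect estimate or uncertainty

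*Combined protocol and SAP*

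**What the plan says.** Section 2.2.6 states the objective as "To determine if Camostat mesilate combined with SOC treatment is associated with reduced duration of" three kinds of support: (a) mechanical ventilation or ECMO, (b) non-invasive ventilation or high-flow oxygen, and (c) "supplemental oxygen use as compared to SOC treatment combined with placebo".

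Section 13.3.2 items 6–8 define the day counts, each within a subset set by baseline ordinal score: 6–7 for ventilator/ECMO days, 5 for non-invasive/high-flow days, and 4 or more for oxygen days.

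Section 13.5 gives the whole analysis of these counts:

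- Item 6: "Duration of ventilator / ECMO use will be summarized by medians or quartiles by arm"
- Item 7: "Duration of non-invasive ventilation / high-flow oxygen will be summarized by medians and quartiles by arm"
- Item 8: "Duration of supplemental oxygenation use will be summarized by medians and quartiles by arm"

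Elsewhere in the same section the plan names a comparison where it wants one. For length of stay, also a count of days, "the number of days hospitalized will be compared between groups by use of non-parametric Wilcoxon rank-sum test". Thrombosis and bleeding "will be described and compared by treatment arms by use of chi-square or Fisher's exact test".

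**The concern.** The objective is directional and comparative. The planned output is two sets of summary statistics side by side, with no treatment effect and no measure of its uncertainty. Item 6 also leaves open whether medians or quartiles are reported.

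Section 13.8 commits the sponsor to reporting the secondary endpoints. With no pre-specified contrast, these durations would be judged by comparing medians by eye, or by a method chosen after the data are known. In the first case a chance gap could be read as benefit, and a real one would have no interval to support it. In the second, the choice of method is open to the criticism that it followed the result.

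**Working it through.** **1. The plan's own figures.** No SD, expected median, subset size, target difference or power is given for the durations, so there is nothing to reproduce for them. The only sample-size figure is for the primary endpoint (Section 13.6: 132 per arm, 80% v 92%, two-sided 0.05, 80% power). Unpooled n = (1.96 + 0.8416)² × (0.80×0.20 + 0.92×0.08) / 0.12² = 7.849 × 0.2336 / 0.0144 = 127.3 per arm. The pooled form gives 131. Power at 132 is 81.4% (unpooled) or 80.6% (pooled). That figure stands, but it concerns a Day 28 proportion and says nothing about days of support.

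**2. Which items in 13.5 have a between-arm analysis?**

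| Item | Endpoint | Between-arm analysis named |
|---|---|---|
| 1 | Alive, free of ventilator/ECMO | Z-test, 95% CI, Cochran-Mantel-Haenszel, logistic model |
| 2 | Time to death | Stratified log-rank, Cox |
| 3 | Time to improvement | Cox hazard ratio, 95% CI |
| 4 | Clinical status | Proportional odds model |
| 5 | Length of stay | Wilcoxon; Z-test and 95% CI for ICU admission |
| 6–8 | Three durations of support | None |
| 9 | Adverse events | Chi-square or Fisher |
| 10 | Thrombosis/bleeding | Chi-square or Fisher |

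Days in ICU, within item 5, are also only described, but no objective in 2.2 asks about them. Item 4 is summarised by arm and then modelled, so summarising by arm in this plan does not itself imply a comparison.

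**3. Does another section supply the contrast?** The t-tests in 13.4 belong to the check of the two arms for imbalance. The subgroup paragraph in 13.5 offers odds ratios and interaction tests. An odds ratio is not a defined contrast for a day count, and subgroup effects do not replace a missing overall effect. The missing-data text carries the last status forward to Day 28 after loss to follow-up or withdrawal, and names no comparison.

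**4. Illustrated precision (assumed inputs).** The 95% half-width for a mean difference is 1.96 × SD × √(2/n), with n per arm. Assume an SD of 6–10 days and n of 30–60, that is 60/264 = 23% to 120/264 = 45% of the trial in a subset.

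- SD 6, n = 60: 1.96 × 6 × √(2/60) = 2.1 days
- SD 10, n = 30: 1.96 × 10 × √(2/30) = 5.1 days

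If a subset held only 5% of patients (264 × 0.05 / 2 = 6.6 per arm), the half-width would be 1.96 × √(2/6.6) = 1.08 SD, or 6.5–10.8 days for the same SDs.

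**5. What a comparison must respect.**

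- *Strata.* Section 5.2 splits severity into scores 3–4 and 5. Item 7 (baseline 5) lies in a single stratum. Item 6 (baseline 6–7) lies in neither, although 3.1.6 admits any score of 3 or more. Severity can vary only in item 8.
- *Deaths.* Days are counted at scores 6–7, 5 or 4–7, and death is score 8 (Section 12.0), so death stops the count. The missing-data rule covers loss to follow-up and withdrawal, not death. A patient who dies early on support is therefore recorded with a shorter duration than one who is supported longer and recovers.

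**The case against.** The best defence is that descriptive reporting of lower-ranked secondary endpoints, in baseline-defined subsets of a phase 2 trial, is legitimate. The baseline 6–7 subset may be very small, and a test there could be uninformative. Related questions about respiratory support do have inferential analyses (items 1, 3 and 4). A comparison added without a rule for deaths could mislead more than medians do, because it could favour the arm with more early deaths.

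Most of this stands, and it shapes the remedy. It does not remove the mismatch: if the durations are meant to be descriptive, 2.2.6 should not be worded as a comparison with placebo. Items 1, 3 and 4 limit the consequence, but none of them estimates duration.

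Three stronger readings are tempting and are not supported:

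- A reader might infer that 2.2.6 cannot be addressed at all. Medians and quartiles by arm are descriptive evidence. What is missing is a planned effect estimate with its uncertainty.
- A reader might gauge precision from 132 per arm. Each of items 6–8 is restricted by baseline score, so that number does not apply to them.
- A reader might ask for one test stratified by age and severity for all three durations. Severity stratification is empty for items 6 and 7 as now defined.

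**Conclusion.** The point holds as an inconsistency between a stated secondary objective and its analysis. For three durations the plan names a method that yields no treatment effect and no measure of uncertainty, and no other section supplies one. This rests on the text alone and on no numerical assumption.

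Its size is only illustrative. A half-width of about 2.1–5.1 days depends on an assumed SD of 6–10 days and 30–60 patients per arm, and it is for a difference in means, whereas the plan reports medians. Under those assumptions an observed gap of one or two days could not be told from chance. The primary endpoint and its sample size are untouched.

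**What to change.** In 13.5 items 6–8:

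- Add for each duration a between-arm difference with a 95% CI, for example Hodges-Lehmann, with the Wilcoxon rank-sum approach already used for length of stay. Keep medians and quartiles as description, and replace the either/or in item 6.
- Stratify by age. Add baseline severity only where it varies: item 8 now, or all three if the baseline restriction is lifted.
- State how deaths enter, so that early death does not count as a shorter duration. Two options are to rank deaths as the worst outcome, or to analyse support-free days to Day 28 with death set to zero. The second keeps the difference on a scale of days; under the first, a shift in days depends on the value assigned to deaths.
- Say in advance that the baseline 6–7 subset will be descriptive if it is too small, and give the threshold.
- Reword 2.2.6 to match for any item that stays descriptive.

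The cost is SAP wording and three more standard analyses, with no new data collection. The drawback is wide intervals in small subsets, which would at least show how little those data can say.

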#### 10.6 Major violation

A patient is deemed a *major violation*, if protocol requirements regarding treatment of the initial therapy are severely violated that evaluability for primary end point is questionable. If the patient received treatment, the patient may continue treatment at the discretion of the physician as long as there are no safety concerns. The patient will continue in the Active Monitoring/Treatment phase of the study, as per section 4.0 of the protocol, and all data submission should continue per protocol. If the patient does not continue with treatment, the patient will go off treatment and be followed in Clinical Follow-up.

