#### 11.1.6 Potential Drug Interactions: Camostat mesilate did not appreciably inhibit CYP1A2, CYP2C9, CYP2C19, CYP2D6 and CYP3A4 (in vitro).

#### 11.1.7 Known potential toxicities:

Clinically significant toxicities:

- Shock or anaphylactic symptoms
- Thrombocytopenia
- Hepatic function disorder or jaundice
- Hyperkalemia

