## 13.0 Statistical Considerations and Methodology

### 13.1 Statistical Design

The study design will be a randomized (1:1 ratio), double-blinded, placebo-controlled phase II trial of 264 patients. Randomization will be stratified based on age (< 65 years versus  $\geq$  65 years) and disease severity at study entry (hospitalized with mild disease versus hospitalized with moderate/severe disease). The purpose of this study is to evaluate the efficacy of Camostat mesilate in addition to SOC treatment as compared to SOC treatment combined with placebo with respect to clinical status on Day 28. The proportion of patients alive AND free from respiratory failure at Day 28 will be the primary outcome.

Patients will be analyzed according to their randomization assignment. All patients meeting eligibility criteria who received at least 1 dose of study drug will be included in the analysis.

Formal interim analysis will be conducted after the first 66 patients (33 treated in the treatment arm and 33 in the control group) have completed the 28 Day assessment period. Safety analyses will be done to assess occurrence of any differences in adverse events between the treatment arms. A second interim analysis will occur after 132 patients (66 in the treatment arm and 66 in the control group) have completed the 28 Day assessment period.

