#### 13.4 Planned Analyses

##### Primary Analysis

Frequency distributions and chi-square tests will be used to screen for major imbalances in the two randomization groups for qualitative variables; graphical displays including box plots and summary statistics (e.g., mean, median, standard deviation, ranges, etc.) will be used for quantitative variables with t-tests (after appropriate transformations if necessary to meet the assumptions of the methods).

The primary outcome will include the number of patients who are alive AND free from respiratory failure at Day 28 divided by the total number of patients in each arm. This endpoint will be analyzed in a binary fashion using properties of the binomial distribution and will be compared between randomized arms by the use of independent samples Z-test for proportions and a 95% confidence interval will be constructed for the difference between arms. Proportions will also be compared using Cochran-Mantel-Haenszel tests, including the stratification factors of age and baseline disease severity. Multivariable logistic regression models will be used to assess the influence of treatment while controlling for covariates of interest (gender, symptom onset, comorbidities) along with stratification factors. Primary analysis for this efficacy outcome will include all participants who are randomized and received at least 1 dose of study treatment. Participants will be analyzed according to the treatment to which they were randomized.

Efforts to minimize loss to-follow-up will be considerable. However, small amounts of missing data may occur. In such cases, participants without Day 28 outcome data will be excluded from the analysis. Sensitivity analyses will evaluate the impact of making different assumptions about the missing observations.

**Interim analyses:** Two interim analyses will be conducted after 25% and 50% of patients have completed the 28 day study period. The interim analysis will include the below stopping rules for efficacy and futility based on a Lan-DeMets spending function with O'Brien-Fleming boundaries. Occurrence of adverse events will also be evaluated at the interim analysis.

Accrual	Control arm (#)	Camostat arm (#)	Total number (#)	Efficacy boundary (Z scale)	Alpha spent	Futility boundary (Z scale)	Beta spent
25%	33	33	66	+/- 4.33	0.001	+/- 0.007	0.002
50%	66	66	132	+/- 2.96	0.003	+/- 0.34	0.04
100%	132	132	264	+/- 1.97	0.05	+/- 1.97	0.20

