### 13.7 Data & Safety Monitoring

The study chair(s) and the study statistician will review the study every week to identify accrual, adverse event, and any endpoint problems that might be developing. A Data Safety Monitoring Board (DSMB) will be formed to monitor the conduct of this study and for reviewing safety data.

The DSMB will be comprised of disease experts who are not investigators or involved with the study. The DSMB will review the study safety data and interim analysis based on reports provided by the Statistical Office.

**Adverse Event Stopping Rules:** The stopping rules specified below are based on the knowledge available at study development. The stopping rule applies to the overall study. We note that the Adverse Event Stopping Rule may be adjusted in the event of either (1) the study re-opening to accrual or (2) at any time during the conduct of the trial and in consideration of newly acquired information regarding the adverse event profile of the treatment(s) under investigation. The study team may choose to suspend accrual because of unexpected adverse event profiles that have not crossed the specified rule below.

Accrual will be temporarily suspended to this study if at any time we observe events considered at least possibly related to study treatment (i.e. an adverse event with attribute specified as “possible”, “probable”, or “definite”) that satisfy the following:

- If 3 or more of the first 10, or 30% or more of patients thereafter (in either treatment arm) experience a grade 3 or higher toxicity considered at least possibly related to study treatment.

- The stopping rule criteria will be evaluated separately for each treatment arm.

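### Section 13.5 item 9 defines the safety set by exposure but groups it by randomised arm, so a mis-supplied patient's adverse events are tabulated under a drug not taken

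*Combined protocol and SAP*

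**What the plan says.** Section 13.5 item 9 sets the safety population by exposure: "Analyses for safety will include all participants who are randomized and received at least 1 dose of study treatment". The next sentence sets the columns by assignment: "Participants will be grouped according to the treatment to which they were randomized". The item then says that "rates of grade 3 or higher events and serious adverse events will be compared between treatment groups using Chi-square" or Fisher's exact test, so the grouping feeds a formal comparison as well as a listing.

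The same grouping appears elsewhere. Section 13.1 gives the general rule, "Patients will be analyzed according to their randomization assignment", with no exception for safety. The primary analysis in section 13.4 uses it for efficacy: "Participants will be analyzed according to the treatment to which they were randomized".

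Section 13.7 adds, for the adverse-event suspension rule, "The stopping rule criteria will be evaluated separately for each treatment arm". It does not say whether an arm means treatment assigned or treatment received.

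Neither these sections nor the missing-data rules in 13.5 say how to tabulate a patient who took the other arm's product, or both products.

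**The concern.** Grouping by randomised arm suits the efficacy comparison: it preserves randomisation, and any dilution from wrong exposure works against claiming benefit. In a safety comparison the same dilution works against seeing harm.

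The safety aim here concerns the drug. Objective 2.2.7 compares the toxicity profile of camostat with that of placebo, both on top of standard care. Item 9 is headed as treatment-related events, and section 8.3 judges attribution against the agent. An event caused by camostat in a patient randomised to placebo but given camostat would be counted for placebo. At stake is the accuracy of the adverse-event tables and their tests, and only if a wrong supply occurs.

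**Working it through.** The plan gives no figure for this point, so there is none to reproduce. The only document number used is 132 per arm (section 13.6), taken here as the size of each safety group. The sample size behind it is not in dispute: 80% versus 92% at two-sided 5% and 80% power gives 131 per arm with pooled variance and 128 with unpooled variance.

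**Assumptions (none is in the documents)**
- Event rates: placebo p0 and camostat p1, at 10% and 20%, or 15% and 30%.
- Wrong supplies: s placebo-randomised patients take camostat and k camostat-randomised patients take placebo.
- Mis-supplied patients are otherwise like the rest, and their event rate follows the drug they took.

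**Formula**
- Placebo column as randomised: [(132 − s)·p0 + s·p1] / 132
- Camostat column as randomised: [(132 − k)·p1 + k·p0] / 132
- Difference as randomised: (p1 − p0) × [1 − (s + k)/132]
- Difference as received: p1 − p0

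If the same fraction m is swapped in each arm, the multiplier is 1 − 2m. So 2% swapped loses 4% of the difference, and 5% loses 10%. At 132 per arm those fractions are about 3 and 7 patients in each arm.

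**One case in full (10% versus 20%, s = 1, k = 0)**
- Placebo column: (131 × 0.10 + 1 × 0.20)/132 = 13.3/132 = 10.08%
- Difference: 20.00 − 10.08 = 9.92 points, against 10.00 as received, a loss of 0.08 point

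**Results** (power is the two-sided 5% normal approximation with pooled variance)

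| Assumed rates | Mis-supplied | Difference as randomised | Difference as received | Power as randomised | Power as received |
|---|---|---|---|---|---|
| 10% vs 20% | 1 placebo patient | 9.9 | 10.0 | 61.7% | 62.4% |
| 10% vs 20% | 3 per arm | 9.5 | 10.0 | 58.5% | 62.5% |
| 10% vs 20% | 7 per arm | 8.9 | 10.0 | 53.0% | 62.5% |
| 15% vs 30% | 1 placebo patient | 14.9 | 15.0 | 82.9% | 83.5% |
| 15% vs 30% | 3 per arm | 14.3 | 15.0 | 79.9% | 83.5% |
| 15% vs 30% | 7 per arm | 13.4 | 15.0 | 74.5% | 83.5% |

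**A single rare event.** Suppose one placebo-randomised patient takes camostat and has the only event of its kind.
- As received, the groups are 133 and 131 and the table is 1/133 versus 0/131. The two possible tables have probabilities 133/264 = 0.504 and 131/264 = 0.496. The observed table is the more likely one, so the two-sided Fisher p is 0.504 + 0.496 = 1.0.
- As randomised, the table is 0/132 versus 1/132. Each possible table has probability 0.5, so p is again 1.0.

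The event changes column, but the planned test does not change its answer.

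**The case against.** The strongest reply is that this is a deliberate and consistent choice. Sections 13.1, 13.4 and 13.5 all group by assignment, nothing contradicts them, and as-randomised safety tables keep the randomised comparison intact. The trigger is also hypothetical: under sections 6.3 and 11, assignments go electronically to a central pharmacy that prepares, labels and ships blinded supplies per patient. No crossover is planned and no error rate is given. All of this stands, and it limits the point to a low-cost improvement.

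A reader might infer more in three ways, and the documents support none of them.

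- **That the protocol expects wrong-arm supply.** Section 10.6 covers cases where "protocol requirements regarding treatment of the initial therapy are severely violated that evaluability for primary end point is questionable". It concerns treatment violations in general and evaluability for the primary endpoint. It does not mention the other arm's product.
- **That the rule conceals camostat's harms.** Section 11.1.7 lists serious toxicities such as "Shock or anaphylactic symptoms". Item 9's table is not the only route by which these would be seen: serious events go to the sponsor whatever their attribution (sections 8.0 and 8.4), grade 3 to 5 events resulting in hospitalisation of at least 24 hours need an initial report within 24 hours, and attribution is made event by event (section 8.3).
- **That one misplaced rare event overturns the safety conclusion.** It changes which column shows the event, but the Fisher p-value is 1.0 either way.

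One part of the concern survives. Individual reporting does not correct the between-arm table, and the final comparison would still place the event under a drug the patient did not take.

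**Conclusion.** The point holds as a minor, conditional one. As written, item 9 would misplace a mis-supplied patient's adverse events and pull the safety difference toward zero, and the plan has no as-received table to show it. The loss is nil without supply errors and about 0.1 point per mis-supplied patient at 10% versus 20%. At those rates it reaches about 0.5 point with three swaps in each arm and 1.1 points with seven, and the documents give no reason to expect that many. The event rates and swap counts are assumptions.

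This is not an internal contradiction and no stated figure is wrong. Efficacy results and the sample size are unaffected. The unclear meaning of arm in section 13.7 is a related wording gap. It is not evidence that the suspension rule would misfire, since that would need a wrong supply at a moment when one event decides the count.

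**What to change.** In section 13.5 item 9:

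- Group adverse events by the study drug actually received.
- Count a patient who took any camostat as camostat for events with onset on or after the first camostat dose. Without this timing rule, events that began before any camostat was taken would be moved to camostat. State where those earlier events are shown and in which denominator.
- Keep the as-randomised table as a sensitivity analysis.

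Leave item 10 as randomised. Objective 2.2.8 frames thrombosis and bleeding as outcomes that camostat may reduce, so an as-received table there should be supportive only. Leave all efficacy endpoints as randomised.

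The cost is a sentence or two, settled before unblinding so that the choice is not made after seeing the data. Drug received would come from supply and dosing records, and item 9 already summarises events by onset date. The downside is that a mis-supplied patient may sit in different groups in the efficacy and safety tables, which a footnote can explain. If no wrong supply occurs, the two safety tables are identical.

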**8.5 Other Required Reporting**

8.5.1 Unanticipated Problems Involving Risks to Subjects or Others (UPIRTSOS) in general, include any incident, experience, or outcome that meets **all** of the following criteria:

1. Unexpected (in terms of nature, severity, or frequency) given (a) the research procedures that are described in the protocol-related documents, such as the IRB-approved research protocol and informed consent document; and (b) the characteristics of the subject population being studied;
2. Related or possibly related to participation in the research (in this guidance document, possibly related means there is a reasonable possibility that the incident, experience, or outcome may have been caused by the procedures involved in the research); and
3. Suggests that the research places subjects or others at a greater risk of harm (including physical, psychological, economic, or social harm) than was previously known or recognized.

Some unanticipated problems involve social or economic harm instead of the physical or psychological harm associated with adverse events. In other cases, unanticipated problems place subjects or others at increased *risk* of harm, but no harm occurs.

8.5.2 Submit via appropriate Case Report Forms the following AEs experienced by a patient and not specified in Section 8.5:

8.5.2.1 Grade 1 and 2 AEs deemed *possibly, probably, or definitely* related to the study treatment or procedure.

8.5.2.2 Grade 3 and 4 AEs regardless of attribution to the study treatment or procedure

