## Appendix I: Clinical Safety Labs

The CBC with differential, comprehensive metabolic panel, and urinalysis tests listed below will be performed at each visit specified in the Test Table (Section 4.0). A renal profile is a subset of the comprehensive metabolic panel, and includes sodium, potassium, chloride, carbon dioxide (total), BUN, creatinine, BUN: creatinine ratio, glucose, and eGFR.

CBC with Differential	Comprehensive Metabolic Panel	Urinalysis
Hematocrit	Alanine aminotransferase	Color
Hemoglobin	Aspartate aminotransferase	Clarity
Mean corpuscular hemoglobin	Alkaline phosphatase	pH
Mean corpuscular hemoglobin concentration	BUN	Specific gravity
Mean corpuscular volume	Creatinine	Bilirubin
Mean platelet volume	BUN:creatinine ratio	Glucose
Platelet count	eGFR*	Ketones
Red blood cell distribution width	Bilirubin, total	Leukocytes
Red blood cell count	Carbon dioxide, total	Nitrite
White blood cell count	Calcium	Blood (hemoglobin)
White blood cell differential (% & absolute):	Chloride	Protein
Basophils	Potassium	Urobilinogen
Eosinophils	Sodium	Red blood cells
Lymphocytes	Glucose	White blood cells
Monocytes	Albumin	Epithelial cells
Neutrophils	Globulin, total	Bacteria, yeast, & parasites
	Albumin:globulin ratio	Casts
	Protein, total	Crystals
	Cholesterol, total	
	Triglycerides	
	Uric acid	

\*eGFR will be calculated as follows:  $eGFR \text{ (mL/min/1.73 m}^2\text{)} = 175 \times (\text{serum creatinine in mg/dL})^{-1.154} \times (\text{age in years})^{-0.203} \times (0.742 \text{ if female}) \times (1.212 \text{ if African American})$

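### No by-arm analysis of post-baseline platelets, liver tests or potassium is planned, and non-serious grade 1-2 changes judged unrelated to treatment do not reach the adverse event tables

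*Combined protocol and SAP*

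**What the plan says.** **Known toxicities.** Section 11.1.7 names, among the clinically significant toxicities of camostat, "Thrombocytopenia", "Hepatic function disorder or jaundice" and "Hyperkalemia".

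**Measurement.** Appendix I puts the platelet count in the CBC, and ALT, AST, total bilirubin and potassium in the metabolic panel. It says these tests "will be performed at each visit specified in the Test Table". In Section 4.0 that means baseline and Days 14, 28 and 56. The renal profile, which contains potassium, is also taken in Days 2-13.

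**Objective.** Section 2.2.7 is "To compare the safety and toxicity profile of Camostat mesilate combined with SOC treatment as compared to SOC treatment combined with placebo".

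**Analysis.** The safety endpoint in 13.3.2 item 9 is grade 3 or higher events and SAEs. Section 13.5 item 9 adds that "Frequency tables of adverse events will be constructed based on maximum grade for each treatment arm", and tests overall event rates, grade 3+ rates and SAE rates with chi-square or Fisher's exact tests. Item 10 covers thrombosis and bleeding. The box plots and t-tests in 13.4 serve only to check balance between the randomized groups.

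**What reaches the adverse event data.** Section 8.5.2 asks sites to submit "Grade 1 and 2 AEs deemed *possibly, probably, or definitely* related to the study treatment or procedure". Grade 3 and 4 events are submitted whatever the attribution.

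**The concern.** The plan names organ-specific harms of the drug and schedules the tests that would show them. It then compares the arms only through events that an investigator chose to submit. For grade 1-2 events that choice depends on attribution. In patients hospitalized with COVID-19 another cause is usually at hand, so a mild platelet fall or a mild transaminase or potassium rise is easily judged unlikely or unrelated. Because the investigator is blinded, this should thin out events about equally in both arms. That does not manufacture a difference, but it removes the events that would reveal one. A statement under 2.2.7 that the arms were similar could then reflect the filter and not the drug.

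**Working it through.** **1. Tracing a low-grade laboratory change through the plan.**

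| Type of change | Required on the CRF? | Source | In the 13.5 item 9 tables? |
|---|---|---|---|
| Grade 3-4, any attribution | Yes | 8.5.2.2 | Yes |
| Grade 1-2, at least possibly related | Yes | 8.5.2.1 | Yes |
| Grade 1-2, causes or prolongs hospitalization by 24 h or more, any attribution | Yes, as an SAE that must also enter routine data | 8.4.1, 8.1(g) | Yes |
| Grade 1-2, non-serious, unlikely or unrelated | No | 8.5.2.1 | No |

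The last row is the gap. Nothing else in Section 13 fills it, because no endpoint, shift table or change-from-baseline summary uses the laboratory values.

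**2. The plan's own figure, used here only for the arm size.** Section 13.6 gives 132 per arm for 80% versus 92%, two-sided alpha 0.05, unpooled variance:

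Φ(0.12 / √[(0.80×0.20 + 0.92×0.08)/132] − 1.96) = Φ(2.853 − 1.96) = 0.814.

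With pooled variance it is 0.806. The stated 80% is reproduced.

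**3. What the attribution filter costs.** The documents give no rates of laboratory abnormality in this population, so the rates below are assumptions. Let c and t be the true grade 1-2 incidence on placebo and camostat, and a the share judged at least possibly related, equal in both arms because of blinding. The tables then see p1 = a·c and p2 = a·t. With n = 132 and p̄ the mean of p1 and p2:

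Power = Φ{ [(p2 − p1)√n − 1.96√(2p̄(1 − p̄))] / √[p1(1 − p1) + p2(1 − p2)] }

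For c = 20% and t = 35%:
- a = 1: (0.15×11.489 − 1.96×0.6315)/0.6225 = 0.780, so power is 0.78.
- a = 0.5: (0.075×11.489 − 1.96×0.4870)/0.4841 = −0.192, so power is 0.42.
- a = 0.25: (0.0375×11.489 − 1.96×0.3578)/0.3569 = −0.758, so power is 0.22.

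| Assumed true rates | All measured changes | Half judged related | A quarter judged related |
|---|---|---|---|
| 10% vs 20% | 0.625 | 0.337 | 0.186 |
| 20% vs 35% | 0.782 | 0.424 | 0.224 |
| 30% vs 45% | 0.714 | 0.344 | 0.180 |

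For 20% versus 35%, the expected patients shown fall from about 26 versus 46 to 13 versus 23 (half) and 7 versus 12 (a quarter). Power is only a yardstick of visibility here: 13.5 item 9 tests overall, grade 3+ and SAE rates, and does not specify a test for each event type.

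**4. What the values themselves could show.** Without baseline adjustment, the mean difference detectable with 80% power is (1.96 + 0.842)√(2/n). That is 0.34 SD if all 132 per arm have a Day 14 value, and 2.802×√(2/80) = 0.44 SD at an assumed 80 per arm. For an assumed 0.4 SD shift, power is 0.90 to 0.96 at 132 per arm and 0.72 to 0.83 at 80 per arm (baseline correlation 0 to 0.5).

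**The case against.** **The attribution bar is low.** In 8.3, an event that may be related already counts as possible, and investigators have the toxicity list in Section 11 before them. The share they would rule out is unknown. This stands, and it is why the working shows a range.

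**A reader might infer that low-grade changes are reported nowhere.** The documents do not support that. Grade 1-2 events that cause or prolong hospitalization are SAEs whatever the attribution and also enter routine data. Remdesivir is in the Section 7.0 treatment table, yet the Schema calls it standard of care, so a rise blamed on remdesivir may or may not count as related to study treatment. Laboratory reports must also be submitted (14.4). The gap is in analysis and tabulation, not in measurement.

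**A reader might infer that maximum grade ignores the baseline value**, since 3.1.7 admits ALT or AST up to 5 × ULN. That is not established. Grading follows CTCAE 5.0, whose handling of an abnormal baseline is not shown in these documents, and item 9 summarises events by date of onset.

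**A reader might compare the laboratory values with grade 3+ events alone.** That would be unfair to the plan, which also tables all submitted events by grade and tests overall rates.

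**The true effect may be small.** The only frequency given for camostat transaminase increases is at least 0.1% and under 0.5%, or 132×0.001 = 0.13 to 132×0.005 = 0.66 expected patients per arm. At such rates neither route would show much. No frequency is given for thrombocytopenia, hepatic disorder or hyperkalemia. The objection limits what the illustration can claim, but does not explain why scheduled data should go unused.

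**Day 14 values will be incomplete.** Patients die or are discharged, and footnote o to Section 4.0 allows remote assessment after Day 1. This stands, so the number measured must be reported.

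**Conclusion.** The point holds in a limited form. Followed as written, the plan makes no by-arm use of post-baseline platelets, ALT, AST, total bilirubin or potassium, and non-serious grade 1-2 changes judged unrelated to study treatment are absent from the safety tables. The comparison under 2.2.7 is therefore insensitive to low-grade harm on organs the plan itself lists as affected by camostat. Serious events, grade 3 and higher events, and low-grade events judged at least possibly related are still captured.

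The size depends on unknown quantities. Under the assumed 20% versus 35%, power falls from 0.78 to 0.42 or 0.22 as the share judged related falls from all to a half or a quarter. This assumes an equal share in both arms and measurement in all 132 per arm. The figures show what the filter can cost; they are not a forecast of camostat's effect. The primary analysis is untouched. This is a worthwhile, inexpensive improvement to a secondary safety objective.

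**What to change.** Add to 13.5 item 9, for platelets, ALT, AST, total bilirubin and potassium:

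- **Shift tables by arm** of baseline grade against worst later grade, derived from the laboratory values and not from the adverse event forms. Show on-treatment samples (through Day 14) separately from Days 28 and 56. Dosing ends at Day 14 and the half-life in 11.1.5 is about 100 minutes, so a single worst post-baseline grade would mix on-drug and off-drug values.
- **The arm difference at Day 14** in the value (log scale where skewed), adjusted for baseline, with a 95% CI and the number of patients with a Day 14 value in each arm.

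Separately, define study treatment for 8.5.2.1 so that Section 7.0 and the Schema agree on whether an event attributed to remdesivir counts as related.

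The cost is a paragraph of analysis text and a few tables from tests already scheduled. The downsides are a few more descriptive safety comparisons without multiplicity adjustment, and some missing Day 14 samples in discharged patients.
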